**Effectiveness of hypnoanalgesia for dermatological surgery in children:
Randomised clinical trial**

NCT CHT00028

Document Date: March 15, 2019

PI: [name]

1 Anaesthesia and Resuscitation Service, Toledo Hospital Complex. Toledo. Spain

[name]

Email: [contact]

Keywords: Hypnosis, hypnoanalgesia, anxiety, pain, paediatric surgery, dermatology

State of the art. Justification.

Since the development of "hypnosedation" by anaesthesiologist Faymonville et al. in 1977¹, the combination of hypnosis and conscious sedation techniques with low-dose intravenous drugs, or local or locoregional anaesthetic infiltration, has demonstrated multiple advantages. These advantages have been observed both in the preoperative phase, given the correlation between preoperative anxiety and postoperative pain^{2, 3}, in the perioperative phase, with efficacy observed in minimally invasive procedures and awake craniotomy^{4, 5}, and in the postoperative phase, with evidence of a reduction in nausea and vomiting, pain and early awakening and discharge^{6, 7}.

Better knowledge of the technique and its greater use in operating theatres has led to the abandonment of the concept of sedation in favour of that of analgesia, which is why the term hypnoanalgesia is now used instead of hypnosedation. Patients treated under hypnosis show greater comfort and lower levels of anxiety^{8, 9}. In addition, the high receptivity and suggestion reached with hypnosis during anaesthesia help to reduce analgesic and sedative doses during and after the surgical procedure, which facilitates recovery^{10, 11}.

Doctors and surgeons in the early 19th century already pointed out that children and adolescents were particularly "sensitive" to hypnotic techniques, showing good response to hypnotherapeutic strategies¹². However, most studies of hypnosis and pain have been conducted in adults. The mechanisms of action proposed for non-pharmacological comprehensive therapies in adults may differ in the paediatric population due to, among other reasons, possible developmental effects, requiring specific studies in that population^{10, 13-15}.

Objectives

The aim of this study is to assess whether the use of hypnoanalgesia in dermatological surgery in the paediatric population reduces

1. the need for sedation and analgesia during the procedure, and
2. its impact on pain

- a. in the immediate post-operative period and
- b. after 24 hours.

Secondary objectives are

1. to assess the degree of acceptance of the procedure and
2. to evaluate the efficacy of the technique according to the age of the patients and, therefore, their suggestibility.

PATIENTS AND METHODS

Design

1:1 parallel group unicenter randomized clinical trial.

Randomisation and masking

Randomisation will be carried out in blocks, depending on the day of the operation (day with hypnosedation or day with distraction), without the dermatologists or the anaesthetist performing the operation having prior knowledge of either the assigned day or the "suggestibility" of the cases, respectively.

The blinding will be achieved by assigning different investigators to each phase of the study, with one designated as responsible for recruitment ([name]), another for intervention and control ([name]), and another for subsequent evaluation in the post-anaesthesia recovery unit (URPA) and at 24 hours (responsible nursing staff).

Participants

Children scheduled for dermatological surgery will be recruited for major outpatient surgery (MOS) at the National Paraplegic Centre.

The following inclusion criteria are established:

1. age between 5 and 16
2. any gender / sex

3. A class I or II of anaesthetic risk according to the American Society of Anesthesiologists,
4. to be in a percentile between P3 and P97 in weight and height,
5. without known drug allergies, and
6. having fasted 6 hours for solids and 2 hours for water.

The following exclusion criteria have been established:

1. mental retardation
2. attention deficit,
3. behavioural disorders,
4. previous treatment with hypnosis,
5. history of neurological pathology or psychomotor retardation,
6. previous pain-related pathology,
7. obstructive sleep apnoea syndrome (OSAS)

Recruitment will be carried out by the principal investigator from the surgical waiting list for a period of 5 months.

All patients who meet the inclusion criteria will be given informed consent and an information sheet, both on the anaesthetic procedure and on hypnosis as an adjuvant technique.

Intervention, control and procedures

Patients will be randomly distributed to one of the following groups:

- *Intervention group*: A technique of rapid conversational hypnosis, with focus on therapeutic suggestion (guiding the patient into a hypnotic trance), adapted to the cognitive development. Induction with hypnotic suggestion focuses and accompanies the child's body sensations and allows their active participation. After standard sedation, therapeutic suggestion is maintained throughout the surgery and in the post-hypnotic period before awakening.
- *Control group*: A high-tech distraction technique (Apple®), passive and chosen by the child, either an animated video or his or her favourite music. After standard

intravenous sedation, the child is taken to the operating theatre to watch his or her favourite video or music and this is maintained throughout the procedure.

Procedures and concomitant treatments

In the previous anaesthesia consultation, the therapeutic alliance is established with all the children, regardless of the group assigned, giving them the opportunity to choose their favourite experience of therapeutic suggestion, according to their age and level of cognitive maturity.

Patients and tutors are given a behavioural therapeutic session to reduce the anxiety and fear associated with the procedure and to eliminate any negative connotations associated with medical hypnosis.

Prior to surgery, the pre-surgical checklist will be completed. The entire surgical team has received training in conversational hypnosis and attention-distracting techniques from the principal investigator, a paediatric anaesthetist, with academic qualifications and experience in clinical hypnosis.

In the anteroom of the operating room, all children will be offered to play, such as with fruit-smelling markers to colour the inside of the anaesthetic mask (Stabylo®).

During surgery, standard sedation will be performed either intravenously or inhalationally as an option. In the endovenous induction, an initial dose of propofol of 2.5 mg/Kg will be injected, registering the additional amount needed. If the additional doses are not sufficient, a short duration opioid, alfentanil, will be administered at a dose of 10-15 micrograms/kg. For inhalation induction, a mixture of nitrous oxide and oxygen (60/40) will be administered at tidal volume with an external Mapelson C circuit (Maquet Flow-i C20®). Finally, the surgeon, in agreement with the anaesthetist, used local anaesthesia with 2% subcutaneous lidocaine.

Waking up will be carried out in the operating theatre with subsequent transfer to the Post-Anaesthesia Care Unit (PACU), where, in addition to control of constants, pain will be assessed using adapted scales (see variables and measurements below), and analgesics will be administered where necessary (if VAS>4 paracetamol will be used, 15 mg/kg, and if pain persisted, magnesium metamizole at a dose of 20 mg/kg).

Evaluation and Outcome Measures

The following outcome variables are established:

- Main variable: Total dose of propofol and additional need for opioids during the operation, measured in mg/kg of weight as recorded intra-operatively.
- Impact on pain and analgesic needs, both in the immediate post-operative period and 24 hours after the operation, measured by pain scales adapted to age and cognitive maturation (Visual Analogical Scale (VAS) from 10 years and Face Drawing Scale or FPS-r from 5 to 9 years), need for paracetamol, ibuprofen or other analgesics. The scales are given to the children by the nurse in charge at the PACU, who will be also responsible for the 24-hour post-surgery follow-up, and did not know the group to which each patient belonged. The analgesic need will be collected from the medical logs.
- Degree of satisfaction with the procedure, using a scale of 1 to 10, administered at the time of discharge from hospital to the children or their guardians.

Statistical analysis

For the descriptive analysis, central tendency and dispersion measures will be used (median and 25th to 75th percentiles, P₂₅₋₇₅) for quantitative variables, and absolute and relative frequencies for qualitative ones. The comparison of the outcome measures between the intervention group and the control group will be carried out by means of non-parametric tests: chi-square and Fisher's exact test for qualitative outcome measures, and Mann-Whitney's U for the quantitative ones.

An age-based subgroup analysis will be conducted (under 7 years and over).

The significance level will be set at a value of $p < 0.05$ and the analysis will be carried out with Excel®.

A sample of 30 patients will be calculated to detect a 40 mg dose difference between the two groups, with a risk α of 0.05 and a risk β of 0.20 in a bilateral contrast and assuming a common standard deviation of 33.3 and a loss to follow-up rate of 10%.

Ethical aspects

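### Treatment appears to be allocated by operating day, but the sample size and the Mann-Whitney test treat the 30 children as independent; if several children share a day and their outcomes are correlated, the 5% level is not held.

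*Protocol*

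**What the plan says.** On allocation, the protocol (Randomisation and masking) states: "Randomisation will be carried out in blocks, depending on the day of the operation (day with hypnosedation or day with distraction". The same sentence describes what is concealed: "without the dermatologists or the anaesthetist performing the operation having prior knowledge of either the assigned day". Read plainly, the day carries the arm, and children operated on together receive the same technique.

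Two other places point towards allocation of individuals. Under Intervention, control and procedures: "Patients will be randomly distributed to one of the following groups". Under Design, the trial is called a 1:1 parallel-group trial, with no mention of clusters. No mechanism for allocating single children is described.

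On analysis, the protocol (Statistical analysis) and the SAP (Statistical plan) agree. Quantitative outcomes, which include the propofol dose in the main variable, are compared by Mann-Whitney U, and qualitative outcomes by chi-square or Fisher's exact test. The sample size is 30, for a 40 mg difference with SD 33.3, two-sided alpha 0.05, beta 0.20 and 10% loss.

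Neither document gives the number of operating days, the children per day, an ICC, a design effect or an analysis term for day. The only indication of scale is under Participants: "Recruitment will be carried out by the principal investigator from the surgical waiting list for a period of 5 months".

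**The concern.** A test of two groups of 15 independent children is valid when children are randomised singly. If whole days are randomised, the independent units are days. Anything that makes children on one list more alike than children on different lists then falls entirely within one arm. Mann-Whitney U counts each child as a separate piece of evidence, so its p-value is too small, and a chance difference between days can be read as an effect of hypnosis. With few days per arm, the planned analysis has no means of separating the two.

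This affects the main variable of a small trial. It also affects power: a valid day-level analysis has fewer degrees of freedom than 30 children suggest.

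**Working it through.** **1. The plan's own figure.** Standardised effect d = 40/33.3 = 1.201.

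- Normal formula: 2 × (1.960 + 0.842)² / 1.201² = 10.9, so 11 per arm; 11/0.9 gives 13 per arm, 26 in total.
- Exact t-test: 12 per arm (power 80.3%); 12/0.9 gives 14 per arm, 28 in total.
- t-test with Mann-Whitney efficiency 0.955: 12/0.955 gives 13; 13/0.9 gives 15 per arm, 30 in total.

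So 30 is reached by a standard formula for independent children. The total alone does not prove this: a t-based size with design effect 1.05 also gives 30 (12 × 1.05 = 12.6, so 13, then 15 per arm). But no design effect is stated, and none is needed to explain the figure.

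**2. Type I error of the planned Mann-Whitney test.** Assumed: whole days in one arm, 15 children per arm, normal outcomes with a random day effect, asymptotic test with continuity correction, 200,000 simulated trials per setting. Children per day and ICC are assumptions.

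| Children per day | ICC 0 | 0.05 | 0.1 | 0.2 | 0.3 |
|---|---|---|---|---|---|
| 2 | 4.6% | 5.1% | 5.5% | 6.5% | 7.6% |
| 3 | 4.5% | 5.6% | 6.7% | 9.1% | 11.5% |
| 5 | 4.6% | 6.6% | 8.9% | 13.6% | 18.2% |

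With 1 child per day it stays between 4.4 and 4.7% whatever the ICC. Five per day means only 6 operating days in the whole trial, an extreme case.

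**3. Scale.** Five months is about 21.7 weeks, and 30/21.7 = 1.4 children a week. Spreading 30 children at random over an assumed 44, 22 or 11 operating days gives 5.0 to 6.7%, 5.4 to 8.9% and 6.1 to 13.2% as ICC goes from 0.05 to 0.3 (100,000 trials each).

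**4. Fisher's exact test.** With assumed event rates of 0.2 to 0.5 and ICC 0.05 to 0.3, it is conservative at 2 per day (1.9 to 3.6%). At ICC 0.3 it reaches about 6% at 3 per day and about 11% at 5 per day. The chi-square test was not assessed.

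**5. Power of a test on day means.** In units of the total variance, a mean of m children has variance v = (1 + (m − 1) × ICC)/m. With k1 and k2 days per arm, the noncentrality is d / √(v × (1/k1 + 1/k2)) on k1 + k2 − 2 degrees of freedom. At ICC 0.1:

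| Layout | Children | v | Noncentrality | df | Power |
|---|---|---|---|---|---|
| 8 v 7 days of 2 | 30 | 0.55 | 3.13 | 13 | 82.4% |
| 7 v 7 days of 2 | 28 | 0.55 | 3.03 | 12 | 79.4% |
| 7 v 6 days of 2 | 26 | 0.55 | 2.91 | 11 | 75.5% |
| 5 v 5 days of 3 | 30 | 0.40 | 3.00 | 8 | 74.9% |

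Part of the drop is lost degrees of freedom: at ICC 0 with 30 children, power is 85.8% at 2 per day and 82.1% at 3.

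**6. Permutation limit.** The smallest two-sided p is 2/C(2k, k) for k days per arm: 2/20 = 0.10 for 3 v 3 days and 2/70 = 0.029 for 4 v 4.

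**The case against.** The strongest reply is that the effect may be very small. At about 1.4 children a week many days may hold one child, and with 44 or 22 operating days the type I error at ICC 0.05 to 0.1 is 5.0 to 6.0%, against a baseline of 4.6 to 4.7%. That stands as a limit on size. It does not remove the point, because children from a waiting list can be grouped onto a few lists and the plan does not say how they are booked.

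The protocol also contains features that argue against a large day effect. There is one centre, a single investigator is named for both intervention and control, and the initial intravenous propofol dose is fixed per kg. These are fair and make a high ICC less plausible, but they do not establish zero. The sedation route is a possible source of day-to-day variation ("standard sedation will be performed either intravenously or inhalationally as an option"), but nothing in the documents links route to day, so this is conjecture.

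The power figures carry two caveats. They use a 40 mg effect, while the main variable is "measured in mg/kg of weight as recorded intra-operatively"; the calculation takes over the plan's own standardised effect without endorsing it. And 80% at 2 per day depends on analysing all 30 children. Intra-operative recording makes that reasonable, but it uses up the plan's 10% loss allowance.

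A reader might infer that the trial's type I error is inflated, even to 18%, or that the trial is definitely cluster randomised. The documents support neither: the first needs inputs they do not give, and the second is contradicted by the wording on distributing patients. Nor may one infer that Fisher's test is safe throughout, since its conservatism is lost beyond 2 per day at the higher ICCs.

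**Conclusion.** The concern holds in conditional form. The only allocation mechanism described is by operating day, and the stated sample size and test do not follow it. Inflation needs all three of whole-day allocation, more than one child on some days, and a non-zero ICC. If any one is absent, the planned Mann-Whitney test keeps its level.

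The documents establish the lack of protection but not its size. For modest assumed correlation and 2 or 3 children per day, the excess over 5% is at most about 2 percentage points; larger figures need stronger clustering than the documents suggest. The stated 80% power is roughly kept by a day-level analysis at 2 per day and ICC 0.1 if nearly all children are analysed, and falls to about 75% at 3 per day. This should be fixed, with medium confidence, because the remedy is cheap and the main variable is affected.

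**What to change.** State the unit of allocation, the number of operating days and the expected children per day. If every day has one child, a sentence saying so is enough. Otherwise choose one of two routes.

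- **Keep day allocation.** Make the primary analysis respect days: a test on day means, or a mixed model with a random day effect and small-sample degrees of freedom. Use a day-level permutation test only with at least 4 v 4 days. Restate the power for 30 children under a stated ICC and number of days. Scheduling does not change. The cost is a slightly less favourable stated power. A test on day means can be run in Excel, the software named in the plan; a mixed model would need another package.
- **Randomise each child individually** with concealed permuted blocks. The planned tests are then valid with no extra patients. The cost is that both techniques must be available on every list, with some risk of carry-over between them: "The entire surgical team has received training in conversational hypnosis and attention-distracting techniques".

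Either route needs a short protocol amendment and matching SAP wording. Whether those who recruit or book children know the day's arm is a separate question of allocation concealment, which a day-level analysis does not settle.

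### Splitting roles does not mask the main variable: propofol top-ups, alfentanil and induction route are left to discretion in theatre, where the arm is very probably known

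*Protocol*

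**What the plan says.** **Masking.** Protocol, Randomisation and masking: "The blinding will be achieved by assigning different investigators to each phase of the study". One investigator recruits, another handles intervention and control, and nursing staff evaluate in the recovery unit and at 24 hours. Allocation goes by operating day and is made "without the dermatologists or the anaesthetist performing the operation having prior knowledge of either the assigned day" or the suggestibility of the cases, with a closing 'respectively' that leaves unclear who lacks which. Under Evaluation and Outcome Measures, the recovery-unit nurse, who also does the 24-hour follow-up, is the only outcome assessor stated not to know the group.

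**Main variable.** Evaluation and Outcome Measures: "Total dose of propofol and additional need for opioids during the operation", in mg/kg, taken from the intra-operative record.

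**Dosing.** Procedures and concomitant treatments: for intravenous induction, "an initial dose of propofol of 2.5 mg/Kg will be injected, registering the additional amount needed". Then: "If the additional doses are not sufficient, a short duration opioid, alfentanil, will be administered", at 10-15 micrograms/kg.

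**Route.** Same section: "standard sedation will be performed either intravenously or inhalationally as an option". The inhaled option is nitrous oxide with oxygen.

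**Techniques.** Intervention, control and procedures, hypnosis arm: "After standard sedation, therapeutic suggestion is maintained throughout the surgery". Control arm: after standard "intravenous sedation, the child is taken to the operating theatre to watch his or her favourite video or music", which also continues throughout the procedure.

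The SAP says nothing about masking, dosing or route.

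**The concern.** The main variable is not a measurement taken on the child after treatment. It is the running total of decisions made by the person giving the drugs. If that person knows the arm and has no fixed criterion for the next dose, expectation can enter the outcome directly. A clinician who believes that hypnosis works may wait longer before a top-up, or may choose the inhaled route more readily. Recorded propofol then falls without any sedative-sparing effect.

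At stake is how the primary result can be read. A lower dose on hypnosis days could mean less need, more restraint or a different mix of routes, and the plan gives no means of telling these apart. It also presents blinding as achieved by an arrangement that does not reach this outcome.

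**Working it through.** **Step 1: who is masked, and when.** The separated evaluator starts in the recovery unit, after the last intra-operative dose, when the main variable is already complete. Theatre staff are denied only prior knowledge. With 'respectively' read literally, the dermatologists do not know the day and the anaesthetist does not know suggestibility. On the most generous reading, both are unaware of both, but only before the operation. Each day then has one technique, that technique runs throughout surgery, and the whole surgical team has been trained in hypnosis and distraction. That the person dosing knows the arm is an inference from these facts; it is not stated.

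**Step 2: where the main variable can differ between arms.** For a child induced intravenously as planned, propofol in mg/kg is

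2.5 + T,

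where T is the sum of top-ups in mg/kg. The 2.5 cancels between arms, so any difference among these children is a difference in T, plus alfentanil. No sedation score, increment or criterion of insufficiency governs either. By contrast, post-operative paracetamol has a numeric trigger (VAS above 4). For a child induced by inhalation, propofol may be far lower or zero; the Protocol does not say whether propofol follows.

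**Step 3: the plan's own figure.** Inputs from Statistical analysis: difference 40 mg, SD 33.3, two-sided α 0.05, β 0.20, 10% loss.

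- Normal formula: 2 × [(1.96 + 0.84) × 33.3 / 40]² ≈ 10.9, so 11 per arm.
- Exact t test: 12 per arm (power 0.803).
- Mann-Whitney allowance: 12 / 0.955 = 12.6, so 13 per arm.
- Loss: 13 / 0.9 = 14.4, so 15 per arm, or 30 in total.

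The planned 30 reproduces and is not in dispute.

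**Step 4: illustration of a dosing shift.** Assumptions: 15 per arm, normal data, no true effect, SD 33.3 taken as mg (no unit is given), and every child in one arm recorded lower by a fixed amount because the arm is known. Test: exact two-sided Mann-Whitney, rejecting if U ≤ 64 (exact size 0.0453), 40,000 simulated trials. The SDs of 20 and 50 mg are assumed, to show the range.

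| Assumed shift | SD 20 | SD 33.3 | SD 50 |
|---|---|---|---|
| 0 mg | 4.5% | 4.5% | 4.5% |
| 10 mg | 24% | 11% | 8% |
| 20 mg | 71% | 32% | 17% |

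The 20 mg shift is half the design difference. The table is in mg because the sample-size inputs are; the main variable is in mg/kg.

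**Step 5: illustration of route.** Assumptions: inhaled children recorded as zero propofol (not stated in the Protocol), 15 per arm, no true effect, tie-corrected Mann-Whitney, 20,000 simulated trials.

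| Inhaled children, one arm vs other | p < 0.05 |
|---|---|
| 1 vs 0 | about 4% |
| 2 vs 0 | about 7% |
| 3 vs 0 | about 11% |
| 5 vs 0 | about 28% |
| 4 vs 1 | about 8% |
| 6 vs 3 | about 4% |
| 8 vs 5 | about 1% |
| 7 vs 2 | about 25% |

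The result depends on the count in each arm and not on the difference alone.

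**The case against.** The strongest reply is that hypnosis cannot be hidden from the theatre team, and that titrating sedation to need is ordinary clinical judgement. Both points are true. But the remedy does not require masking the team. When the dose is the outcome and the doser cannot be masked, a pre-set common rule is the practical safeguard.

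Second, much is already standardised: the starting dose, the order of escalation, the alfentanil range and the recording of additional amounts. This stands and narrows the point. What is missing is the trigger, the route rule, and the time and reason for each dose.

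Third, no text says that the doser knows the arm, and a separate investigator is assigned to intervention and control. This limits confidence, but the stated restriction concerns prior knowledge and the technique is present throughout.

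Fourth, the shifts in the illustration come from no document. That also stands: the table shows how sensitive the test is to biased dosing, not how biased this trial would be.

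Two stronger readings are tempting. From the route table a reader might infer that any imbalance of three inhaled children is damaging. That holds only if the other arm has none; 6 vs 3 and 8 vs 5 do not exceed the nominal rate. A reader might also infer from the wording for the two arms that route was fixed differently by design. The control text does specify intravenous sedation and the intervention text does not, but the general procedure offers both routes to all children. Route could differ by arm; the documents do not show that it would.

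**Conclusion.** The point holds as a gap in design and in the description of masking. The blinding described covers post-operative assessment by staff; it does not cover the main variable. Top-ups and alfentanil have an order but no trigger, and route has no rule, so arm-dependent dosing is possible within the plan as written.

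The size of any bias is unknown. Under the stated assumptions, an arm-related shift of 10 to 20 mg would raise the false-positive rate from about 4.5% to about 11% to 32%. Three inhaled children in one arm and none in the other would raise it to about 11%, if they receive no propofol. The conclusion rests on the inference that the doser knows the arm, which is very probable but not documented. A reader might go further and infer that dosing was in fact biased or that a positive result would be spurious; nothing in the documents shows either.

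This should be corrected: it concerns the primary outcome and is cheap to improve. Confidence is medium.

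**What to change.** 1. Before the first case, set one trigger for propofol top-ups and alfentanil, and one route rule (for example intravenous by default, with listed clinical exceptions). Both should be identical in the two arms, with clinical content decided by the investigators.
2. Reword the masking section to say that the main variable is unmasked and that the stated blinding of staff covers only the post-operative assessment. Carry this limit into the trial's conclusion.
3. Add route, and the time and reason for each dose, to the amounts already recorded on the anaesthetic record. Report route and top-ups by arm.

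**Cost.** Protocol wording, agreement within the team, and a few more entries on an existing record; no extra patients or staff. Clinicians lose some freedom over dosing and route, and the statement of blinding becomes less favourable. Because the trigger would be judged and the reasons recorded by unmasked staff, bias is reduced and made visible, not removed.

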**Effectiveness of hypnoanalgesia for dermatological surgery in
children: Randomised clinical trial**

NCT CHT00028

Document Date: March 15, 2019

Statistical plan

For the descriptive analysis, central tendency and dispersion measures will be used (median and 25th to 75th percentiles, P_{25-75}) for quantitative variables, and absolute and relative frequencies for qualitative ones.

The comparison of the outcome measures between the intervention group and the control group will be carried out by means of non-parametric tests: chi-square and Fisher's exact test for qualitative outcome measures, and Mann-Whitney's U for the quantitative ones.

An age-based subgroup analysis will be conducted (under 7 years and over).

The significance level will be set at a value of $p < 0.05$ and the analysis will be carried out with Excel®.

A sample of 30 patients was calculated to detect a 40 mg dose difference between the two groups, with a risk α of 0.05 and a risk β of 0.20 in a bilateral contrast and assuming a common standard deviation of 33.3 and a loss to follow-up rate of 10%.

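### Pain is measured on FPS-r or VAS according to age, but the plan does not say how the two scales are combined; the test it names would rank them together, which can cost power and exposes a 30-patient trial to age imbalance.

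*Protocol*

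**What the plan says.** - Protocol, Evaluation and Outcome Measures: pain is assessed "both in the immediate post-operative period and 24 hours after the operation", using the "Visual Analogical Scale (VAS) from 10 years and Face Drawing Scale or FPS-r from 5 to 9 years".
- Protocol, Participants: eligibility is "age between 5 and 16", so both instruments will be in use.
- Protocol, Statistical analysis, and SAP, Statistical plan: one generic sentence covers every numeric outcome, "Mann-Whitney's U for the quantitative ones". Neither document describes a conversion between scales, an analysis by instrument, stratification or age adjustment.
- Same sections: "An age-based subgroup analysis will be conducted (under 7 years and over"). This cut is at 7 years, while the instrument changes at 10.
- Protocol, Design and Randomisation and masking: the trial is a "1:1 parallel group unicenter randomized clinical trial", and "Randomisation will be carried out in blocks, depending on the day of the operation". No stratification by age is mentioned.

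**The concern.** A rank test assumes that the values being ranked are comparable. Here a 7-year-old's FPS-r score and a 12-year-old's VAS score would enter one ranking, and nothing in either document shows that equal numbers mean equal pain. Because age determines the instrument, any difference in level between the scales, or between younger and older children, becomes extra spread in the pooled scores.

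The planned subgroup does not resolve this. Children under 7 are all on FPS-r, but the older group combines FPS-r (7-9) with VAS (10-16).

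Pain in the immediate postoperative period and at 24 hours is part of the trial's stated aim. At stake are the power of those comparisons, and how well they withstand an uneven age split in a small trial allocated by operating day.

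**Working it through.** **The plan's own figure.** The only sample-size calculation concerns propofol dose: difference 40 mg, SD 33.3, two-sided α 0.05, β 0.20, 10% loss. The normal formula gives 2 × (1.960 + 0.842)² × (33.3/40)² = 10.9, so 11 per arm; the t-based version needs 12. Dividing 12 by 0.955 (Mann-Whitney efficiency under normality) gives 12.6, so 13. Dividing 13 by 0.90 gives 14.4, so 15 per arm, or 30 in total. The stated 30 is therefore reproducible, but it says nothing about power for pain.

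**Assumptions for pain.** The documents give no pain SD, effect, FPS-r scoring, age mix or offset between scales. Assumed here: 15 per arm; ages uniform over 5-16, so 5/12 on FPS-r; both scales 0-10; VAS in whole points and FPS-r in steps of 2; within-scale SD 1.7; true effect 1.8 points; offset 0 to 3 points.

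**Why pooling costs power.** An offset δ adds variance p(1−p)δ² with p = 5/12, that is 0.243δ². The pooled SD is √(1.7² + 0.243δ²).
- δ = 0: SD 1.70, standardised effect 1.8/1.70 = 1.06
- δ = 2: SD √(2.89 + 0.97) = 1.96, standardised effect 0.92
- δ = 3: SD √(2.89 + 2.19) = 2.25, standardised effect 0.80

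**Simulated power.** The stratified test is van Elteren's: within each instrument stratum k of N_k children, the arm's rank sum minus its expectation, weighted by 1/(N_k + 1), summed over strata and divided by its standard error.

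| Offset (points) | Pooled Mann-Whitney | Stratified by instrument |
|---|---|---|
| 0 | 75% | 73% |
| 1 | 73% | 74% |
| 2 | 64% | 75% |
| 3 | 50% | 72% |

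Repeat runs agree to within about 2 percentage points. A second set of assumptions (SD 2, effect 2, half the children under 10) shows the same pattern: 71% versus 69%, 69% versus 69%, 60% versus 69%, and 51% versus 67%.

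**Overall error rate, no true effect.** With individual randomisation the pooled test keeps its size: 4.3-5.3% under the first set of assumptions and 4.5-5.4% under the second, with a mean difference of about 0.

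**Error rate given an imbalance, no true effect.** With 9 versus 4 younger children the spurious mean difference is about (9 − 4)/15 × δ: 0.67 points at δ = 2 and 1.0 at δ = 3. The pooled test then rejects in about 12% and 16% of trials (10-12% and 14-16% across runs), against about 5% stratified. With 8 versus 5, the pooled rate stays near 5%.

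**How likely is such a gap?** Two independent Binomial(15, 5/12) counts differ by 5 or more with probability 9.4%. If exactly 15 of 30 children are under 10, the probability is 14%.

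**Allocation by day.** The documents do not say how many children are treated per day or whether ages cluster. Assuming 3 per day and strong clustering of age (intraclass correlation 0.4), the pooled test's unconditional error rate is 5.7%, 6.5% and 8.0% at offsets of 1, 2 and 3 points; stratified, it stays at 4.7-5.0%.

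**The case against.** The best defence has four parts.

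1. **Pooling is not stated.** This is right. The documents have one generic sentence for numeric outcomes and never say that the scales are ranked together. It is the natural reading, since no stratum is named, but it is an inference. The firm finding is the omission, and the remedy is the same on either reading.

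2. **Randomisation protects the comparison.** Also right, for individual randomisation. Age precedes allocation and the instrument follows age identically in both arms. A reader might infer that scale differences bias the estimated treatment effect; the calculations do not support that.

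3. **The harm needs unfavourable conditions.** Largely right. At offsets of 0-1 point the two tests are equivalent to within simulation error. Material error inflation needs both a gap of about 5 younger children and an offset of 2-3 points. A reader might infer that any age imbalance would show up as a pain difference; the 8 versus 5 result contradicts this. The defence is weaker for allocation by operating day, where a balance of ages cannot be assumed.

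4. **Pain does not drive the trial.** The main variable and the sample size rest on propofol. This limits the priority of the point, but pain remains part of the stated aim.

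A reader might also think that the plan compares pain levels between age groups. It does not: the secondary objective concerns efficacy by age, that is, the treatment effect within age groups.

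**Conclusion.** The point holds as a gap in the analysis plan with a conditional cost. That there are two age-determined instruments, one unstratified test and a subgroup cut that does not separate the scales is plain from the text.

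The size of the harm is less certain, because it depends on an offset that the documents do not give. Over an assumed 0-3 points, the change in power from pooling runs from nothing (a gain of about 2 points at no offset) to a loss of about 22 points (50% versus 72%). False positives reach about 12-16% only after an imbalance as large as 9 versus 4 and an offset of 2-3 points. The documents do not support a claim of systematic bias or of a generally inflated error rate.

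This should be corrected because the change is cheap, but it ranks below matters that touch the main variable.

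**What to change.** Add to the SAP, and to the protocol's Statistical analysis section: pain at each of the two time points will be compared between arms with a Wilcoxon rank-sum test stratified by instrument (van Elteren; strata FPS-r at 5-9 years and VAS at 10-16 years). Use the same test in the subgroup of 7 years and over; the under-7 subgroup has one instrument and needs no stratification. Report medians and quartiles by arm separately for each scale.

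A justified common metric would be an alternative, but the documents offer no basis for one.

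The cost is about 1-2 percentage points of power if the scales agree, and possibly software other than the Excel named in the plan. The sample size and the analysis of propofol dose stay as they are. Fixing the rule in advance also removes a later choice about how to combine the scales.
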